7.3. Multiple Comparisons and Multiplicity

In order to control for multiple comparisons, the primary and key secondary efficacy analyses will be tested using a fixed-sequence strategy to maintain the overall Type I error rate at 0.05. Each test in the fixed-sequence, uses a 2-sided test at the 0.05 level of significance and starts with the primary efficacy analyses. The first comparison to be assessed for significance is the primary efficacy endpoint analysis of the high-dose group (50 mg TVB-2640) compared to placebo and if statistically significant, testing will proceed to the low-dose group (25 mg TVB-2640) comparison. If both comparisons of the primary efficacy endpoint are significant, then testing will proceed to the key secondary efficacy endpoint. The key secondary efficacy analyses will be tested in a similar fashion, first comparing the high dose group (50 mg TVB-2640) with placebo and if statistically significant, testing will proceed to the low dose group (25 mg TVB-2640) comparison.

7.4. Reference Dates

- Screening date is defined as the electronic case report form (eCRF) provided date on which a subject was screened for study entry.

- Randomization date is defined as the date on which the subject is randomized to study treatment.
- Treatment start date is defined as the date of first dose of study drug (also referred to as Day 1).
- Treatment end date is defined as the date of last dose of study drug.
- The calculation of age will use the screening date as its reference date.
- Safety data, such as AEs and laboratory assessments will use the treatment start date as a reference date to assign treatment emergence.
- Study day will be based on treatment start date as a reference date.

Reference day calculations will be defined as:

- date of interest – reference date + 1 when the date of interest \geq reference date;
- otherwise, date of interest – reference date.

For example, duration of treatment is defined as treatment end date – treatment start date + 1.

If either date is missing, reference date calculations will not be performed. Date imputation will be performed as identified in Section 7.6.

7.5. Baseline and Post-Baseline Changes

Unless stated otherwise, baseline will be based on the last non-missing value collected prior to the start of study treatment based on the treatment start date and time, if applicable. Post-baseline values will be those collected after the treatment start date and time, if applicable.

Change from baseline is defined as:

$$\text{post-baseline value} - \text{baseline value}.$$

Percentage change from baseline is defined as:

$$(\text{post-baseline value} - \text{baseline value})/\text{baseline value} \times 100\%.$$

7.6. Imputation of Partial Dates

Imputed dates will be used to classify treatment emergent AEs (TEAEs) and prior and concomitant medications.

Adverse Events

- If the AE start date is completely missing the event will be assumed to have started on the first day of treatment and will be considered a TEAE. If a subject was not treated, then no imputation will be conducted for missing start dates.
- If the AE start date is missing day and month, do the following:
 - If the AE start year is the same year as that of the first treatment and the AE contains information to indicate that the event ended before the treatment start

Sponsor: Sagimet Biosciences

Protocol Number: 3V2640-CLIN-005

Version and Date: Final Version 1, 02June2020

date (e.g. AE end date month and year are earlier than the treatment start date or the full AE end date is known and occurs earlier than the treatment start date), then set the AE day/month to '1 January'.

- If the AE start year is the same as that of the first treatment and the AE contains information to indicate that the event ended after the treatment start date, then set the AE start day/month to the treatment start day/month
- If the AE start year is later than that of the first treatment, then set the AE start day/month to '1 January.'
- If the AE start year falls before that of the first treatment, then the AE start day/month will not be imputed.
- If only the AE start day is missing, do the following:
 - If the AE start year is the same year as that of the first treatment and the AE month is prior to the first treatment date, then set the AE day to '1'.
 - If the AE start month/year are the same as that of the first treatment and the AE contains information to indicate that the event ended before the treatment start date (e.g. the full AE end date is known and occurs earlier than the treatment start date), then set the AE day to '1'.
 - If the AE start month/year are the same as the first treatment and the AE end date is after the treatment start date, then set the AE day to the same day as treatment start day.
 - If the AE start year is the same as that of the first treatment and the AE start month is after the first treatment, or the AE start year is later than that of the first treatment, then set AE day to '1'.
- AE end dates will not be imputed.

Prior and Concomitant Medications

- The imputation rules for AE start dates will be used for prior and concomitant medication start dates.
- Prior and concomitant medication stop dates will be imputed as follows:
 - If the stop date is only missing the day, then the stop day is the last day of the month
 - If the stop date is missing both the day and month, then the stop month and day is December 31
 - If the stop date is completely missing, no imputation is performed, and the medication will be classified as a concomitant medication for subjects who were treated.

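### SAP 7.6 counts an AE with no start date as treatment-emergent even if it ended before first dose, and leaves some ongoing AEs with a partial start date unclassified

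*SAP*

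**What the plan says.** SAP 7.6 states its purpose: "Imputed dates will be used to classify treatment emergent AEs (TEAEs) and prior and concomitant medications".

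For a completely missing AE start date, "the event will be assumed to have started on the first day of treatment and will be considered a TEAE". One exception follows: "If a subject was not treated, then no imputation will be conducted for missing start dates". The end date is not mentioned.

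For partial start dates, the end date matters only when the known part of the start coincides with first dose:

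- **Day and month missing, first-dose year.** If the event ended before treatment, the start becomes 1 January. The other branch requires "information to indicate that the event ended after the treatment start date, then set the AE start day/month to the treatment start day/month".
- **Day missing, first-dose month and year.** If the event ended before treatment, the day becomes the first of the month. The other branch begins "If the AE start month/year are the same as the first treatment and the AE end date is after the treatment start date" and then uses the first-dose day.

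The rules for an earlier month in the first-dose year, for a later month and for a later year need no end date. An earlier year with day and month missing is deliberately not imputed. Finally, "AE end dates will not be imputed".

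SAP 8.5.1 defines a TEAE as an AE that occurs after the first dose, and restricts all AE summaries to TEAEs.

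**The concern.** There are two defects.

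The first is a stated rule that gives a wrong answer. If the start date is blank but the end date shows that the event was over before dosing, the event cannot be treatment-emergent. The rule still starts it on Day 1, after its own recorded end, and counts it. The partial-date rules a few lines below do consult the end date, so the omission is out of line with the rest of the section.

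The second is a gap. Where the known part of the start date coincides with first dose, the branches depend on when the event ended. An ongoing AE has no end date, and 7.6 supplies none. An event ending on Day 1 itself is neither before nor after treatment start. These are the records whose classification is truly in doubt, and the programmer would have to choose.

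The TEAE flag decides which events enter every AE table. Safety is a primary objective (SAP 2.1), and the proportion of subjects with TEAEs is a safety endpoint (SAP 4.2).

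**Working it through.** The plan gives no figure to reproduce. The check applies SAP 7.6 literally to each combination of start-date completeness and end-date status, then compares the result with the true class.

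**Inputs**
- Imputation rules: SAP 7.6. TEAE definition: SAP 8.5.1.
- AEs are collected from consent (Protocol 12.2.1.1), and screening may begin up to 60 days before randomization (Protocol 7.1). An AE that ended before first dose can therefore be in the database.
- First-dose date: 15 June 2019, an illustrative assumption. True starts tried: 20 December 2018, 1 May, 5 June, 20 June and 10 August 2019, and 10 January 2020.

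**Result of the literal rules**

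| Known part of start | Ended before first dose | Ended on Day 1 | Ended after Day 1 | Ongoing |
|---|---|---|---|---|
| Nothing | Day 1, TEAE (wrong) | Day 1, TEAE | Day 1, TEAE | Day 1, TEAE |
| Year only, first-dose year | 1 January, not TEAE | no rule | Day 1, TEAE | no clear rule |
| Month and year, first-dose month | first of month, not TEAE | no rule | Day 1, TEAE | no rule |
| Month and year, earlier month of first-dose year | first of month, not TEAE | same | same | same |
| Month and year, later month or year | cannot occur | cannot occur | first of month, TEAE | same |
| Year only, later year | cannot occur | cannot occur | 1 January, TEAE | same |
| Year only, earlier year | not imputed, evidently pre-dose | same | same | same |

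**Reading the table**
1. *Start missing, ended before first dose.* All 3 feasible true starts (20 December, 1 May, 5 June) are classed as TEAEs; all 3 are truly pre-dose. With a missing start and a later or absent end date, counting is a reasonable default because the onset is unknown.
2. *Ongoing, year only, first-dose year.* All 4 true starts receive no date on a literal reading. Two began before dosing and two after.
3. *Ongoing, day missing, first-dose month.* Both true starts receive no date. One began before dosing and one after.
4. *Ended on Day 1.* The same two rows have no branch for this.
5. *All other ongoing AEs with a partial date* are placed correctly or are self-evident. A day-missing start in an earlier year has no rule, but its class is obvious.

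**Size per subject.** One subject reclassified in a planned arm of 30 moves an incidence row by 1/30 = 3.3 percentage points. In the 50 mg arm with China included (planned 48) it is 1/48 = 2.1 points. These are ceilings: if the subject already has another event counted in that row, the change is zero.

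**The case against.** The best defence is that the SAP counts an event when in doubt. Missing severity becomes Grade 3 and missing relationship becomes related (SAP 8.5.1), and a completely missing medication stop date makes the medication concomitant (SAP 7.6). On that view the missing-start rule is a conservative default that lacks one exception. This is a fair description, but conservatism is for uncertainty, and a recorded end before first dose removes it.

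The affected records should also be rare. Onset date is a required AE item (Protocol 12.2.3), missing data must be explained (Protocol 15.2) and source data are verified (Protocol 15.1). SAP 8.5.1 sends clinically significant pre-dose findings to medical history. Safety has no formal testing, and every AE is listed with non-TEAEs flagged, so no event vanishes from the report. All of this stands and keeps the point minor.

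For the year-only branch, 7.6 asks for information about when the event ended, not for an end date as such. An ongoing flag might be taken to satisfy it, so that cell is unclear rather than empty. The day-missing branch names the end date itself and leaves no such room.

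A reader might go further and infer that events are misclassified in both directions, with early unresolved events dropped from the tables. The text does not say so. Dropping them would need a programming default that the SAP does not state and that runs against its usual convention. Nor does SAP 7.4 supply it. Its sentence "If either date is missing, reference date calculations will not be performed" concerns study-day and duration arithmetic, and the sentence after it refers date imputation to 7.6. A reader might also expect negative AE durations in the listings. SAP 8.5.1 plans no AE duration, and 7.6 uses imputed dates for classification only.

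**Conclusion.** The point holds as a minor drafting defect in two parts. The missing-start rule over-counts, as written, any AE recorded as ending before first dose. The partial-date rules leave unclassified an AE that is ongoing or ended on Day 1 when the start day is missing in the first-dose month. They are unclear or silent for the same AEs when only the first-dose year is known. The wider inference that every ongoing AE with a partial date lacks a start date is not supported: earlier-month, later-month and other-year starts are handled or self-evident.

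The number of affected events cannot be derived from the documents and may be zero. Per affected subject the ceiling is 3.3 percentage points in an arm of 30, on the planned arm size. The direction of any effect from the second gap depends on a programming choice not yet specified. Efficacy analyses are unaffected.

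**What to change.** Amend SAP 7.6 with two clauses:

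- **(a) Completely missing start date, treated subject.** Impute the treatment start date and count the event as a TEAE, unless a full or partial end date shows that it ended before the treatment start date. In that case it is not a TEAE.
- **(b) Partial start date that cannot be placed relative to first dose.** This applies only when the month is unknown and the year is the first-dose year, or when the day is unknown and the month and year are those of first dose. Set the start to the treatment start date unless the end date shows that the event ended before it. Ongoing AEs, missing end dates and an end date on Day 1 then count as TEAEs.

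Leave the earlier-month, later-month and other-year rules unchanged. Clause (b) must keep its restriction: without it, an ongoing AE known to have begun in an earlier month of the first-dose year would be moved to Day 1 and wrongly become a TEAE.

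The cost is two clauses in the SAP and a few lines of code, with no change to data collection.

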7.7. Multiple Assessments and Visit Windows

Nominal visits (e.g. those identified by the study eCRF) will be the basis of summarization and statistical analysis; no visit date windowing will be conducted. Unless specified otherwise, data from unscheduled visits will be included in: (1) summaries of most extreme and baseline data, (2) summaries of specific abnormalities at any time post-baseline, (3) adverse events and any other summaries not based on study visit, and (4) subject data listings.

7.8. Missing Data

Imputation will only be performed on the primary and selected secondary efficacy endpoints using MRI-PDFF data.

In the primary and key secondary analyses, missing Week 12 values for MRI-PDFF will be imputed with the last post-baseline observation on or after Week 8. For sensitivity analyses that include subjects with extended dosing, the End of Treatment values for MRI-PDFF will be imputed with the last post-baseline observation on or after Week 8.

MRI-PDFF analyses at other timepoints (e.g., End of Study) will follow similar conventions and use the last-post baseline observation on or after Week 8. Missing MRI-PDFF data before Week 8 will not be imputed.

Sensitivity analyses will be performed excluding data from subjects with missing data (i.e., observed cases approach).

Additional details are provided in the relevant analysis sections below.

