Lymphocyte subsets in peripheral blood mononuclear cells (Cohorts 1 and 2 only) ^{22,26}		X						X		
Sample for storage ^{22,27}		X						X	X	
Spot urine sample collection for:										
Exploratory PD biomarkers ²²		X						X	X	
Study Drug Administration										
Randomization		X ²⁸								
Study drug dispensation		X			X	X				
Study drug administration		QD PO from Day 1 through Week 12								
Study drug accountability				X	X	X	X	X		

Table footnotes appear on the following page.

- 1 Baseline evaluations are to be performed pre-dose, unless otherwise specified.
- 2 At the time of this amendment, subject participation in the 25 mg cohort is complete, with participation in the 50 mg cohort fully enrolled but with subject participation ongoing. The Sponsor notes that the COVID-19 pandemic may impact the conduct of the 50 and 75 mg cohorts, with challenges potentially arising from quarantines and travel limitations affecting study subjects as well as clinic and imaging facility closures. Accordingly, safety assessments scheduled for the Week 12 and 16 visits, including sample collection for clinical laboratory tests, physical examinations, and documentation of AEs, may be performed at an alternate study center or by home health care visit. Furthermore, if the subject is unable to attend the Week 12 visit at the study center, one MRI-PDFP may be performed at any time between Week 11 and 16. If this scan is performed after Week 12, the subject must continue to receive study drug until the final scan is performed; however, study drug is not to be continued for >16 weeks. The safety of subjects who continue dosing beyond 12 weeks will be assessed during this continued dosing period by planning for blood sample collection at an alternate site or home visit at Week 12 and blood sample collection and physical examination on the last day of dosing. A 4-week off treatment safety assessment is to occur after the last dose, regardless of whether a subject receives treatment for 12 or 16 weeks.
For subjects in Cohort 3, Week 16 assessments may serve as screening assessments if within the window before the Day 1 visit.

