- 12 Baseline liver aminotransferases are to be the mean of at least 2 values taken at least 4 to 12 weeks apart; the first measurement may be a historical measurement.
- 13 Fasting clinical chemistries include chloride (Cl), carbon dioxide (CO₂), sodium (Na), potassium (K), blood urea nitrogen (BUN), calcium, magnesium, creatinine, albumin, alkaline phosphatase (ALP), total bilirubin, indirect and direct bilirubin, and total protein. Creatine phosphokinase (CPK) (total and fractionated) is to be calculated during screening and at baseline.
- 14 Urinalysis includes specific gravity, pH, blood, glucose, protein, ketones, and microscopic examination of sediment.
- 15 For female subjects of child-bearing potential only; subjects with positive results are to discontinue study drug immediately.
- 16 Baseline imaging studies may be performed within 28 days before Day 1.
- 17 Due to the COVID-19 pandemic, if the subject is unable to attend both the Week 12 and Week 16 visit, one MRI-PDFP may be performed at any time between Week 11 and 16. If this scan is performed after Week 12, the subject must continue to receive study drug until the final scan is performed. However, study drug is not to be continued for >16 weeks.
- 18 Note that subjects without a biopsy performed within 24 months of randomization MUST have MRE performed during screening.
- 19 Fasting lipid panel includes LDL-C, non-LDL-C, HDL-C, non-HDL-C, total cholesterol, triglycerides, ApoB, and Lp(a) particles.

- 20 Fasting metabolic panel includes glucose, insulin, NEFA, and GGT. HOMA2-IR and adipo-IR are to be calculated from fasting insulin, fasting glucose, and fasting NEFA, as applicable.
- 21 NASH and fibrosis biomarkers include CK-18, FIB-4 Index, ELF (TIMP-1, PIIINP, HA), PROC3, and FIBROSpect 2. For Cohort 3 (75 mg), only PROC3 sample will be collected.
- 22 For Cohort 3 (75 mg), these samples will not be collected as dedicated blood collections. Instead, assays for some of these parameters may be conducted retrospectively using additional aliquots collected from the “NASH/fibrosis markers sample” or from the “lipidomic analyses for DNL sample”.
- 23 The genomics sample collection is optional for Cohort 3 (75 mg).
- 24 [REDACTED]
- 25 [REDACTED]

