drug was not permitted to be continued for more than 16 weeks. For these subjects, the End of Study Visit was scheduled for 4 weeks after the last dose of study drug. For purposes of consistent terminology in context of the COVID changes, the following terminology will be used,

End of Treatment Visit: Visit performed following the end of study treatment. This will be the Week 12 visit for subjects who completed the treatment period as planned. For subjects who entered extended dosing, the visit will be performed on or prior to Week 16. For subjects who received less than 12 weeks of study treatment, the visit will be prior to the scheduled Week 12 visit.

End of Study Visit: Visit corresponding to 4 weeks after the end of treatment visit. This will be the Week 16 visit for subjects who completed the treatment period as planned.

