4. STUDY ENDPOINTS

4.1. Efficacy

The primary efficacy endpoint is:

- Percent change from baseline in liver fat at Week 12, as determined by MRI-PDFF.

The key secondary efficacy endpoint is:

- The percentage of subjects with at least a 30% reduction in liver fat at Week 12, as determined by MRI-PDFF.

Additional secondary efficacy endpoints are:

- Percent change from baseline in liver fat at End of Treatment and End of Study, as determined by MRI-PDFF.

Sponsor: Sagimet Biosciences

Protocol Number: 3V2640-CLIN-005

Version and Date: Final Version 1, 02June2020

- Percentage of subjects with at least a 30% reduction in liver fat at End of Treatment and End of Study, as determined by MRI-PDFF.
- Change from baseline over the treatment period in:
 - Liver aminotransferases.
 - Lipid and lipoprotein parameters.
 - NASH and fibrosis markers.
 - Eicosanoids.

Exploratory efficacy endpoints are:

- Change from baseline over the treatment period in:
 - Liver fibrosis, as determined by VCTE.
 - Metabolic parameters.
 - Anthropometric parameters.
 - Lipidomic analyses for DNL.
- Proportion of subjects with <5% liver fat (normalized) at Week 12.

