Similar responder analyses will be performed using response level definitions of 20%, 40%, and 50%. As done for the key secondary endpoint efficacy endpoint, subjects with a reduction of at least 19.5%, 39.5%, and 49.5% from baseline, respectively, will count as responders. Analyses will be repeated in the ITT, ATP, and PP populations. Analyses of the key secondary endpoint performed in the ATP populations will include summaries of all subjects in the analysis population, as well as the subset of subjects that have at least 8 weeks of treatment and an evaluable assessment on/after 8 weeks (i.e., the same subjects in the mITT population).

Similar responder analyses will be performed using reduction in liver fat at End of Study in the mITT, ITT, and ATP populations.

A scatter plot of End of Treatment body weight changes versus End of Treatment liver fat changes will be graphed by treatment and overall in the ATP. A subset will also be run in subjects with at least a 30% reduction in liver fat at Week 12.

In the key secondary analysis, missing Week 12 values for MRI-PDFF will be imputed with the last post-baseline observation on or after Week 8 in the mITT population. Sensitivity analyses excluding subjects with missing data will also be performed.

Other Efficacy Endpoints

Other efficacy endpoints will be summarized using the ATP. A limited set of endpoints will be repeated in the ITT.

Liver aminotransferases will be evaluated using observed values and changes from baseline by study visit. Summaries will be performed for ALT and AST and will be presented by treatment group.

The changes at 12 weeks will be summarized for each treatment group and compared between each TVB-2640 dose group and pooled placebo using a linear mixed-effects model for repeated measures (MMRM). The model will include the stratification factor (diabetes presence/absence),

Sponsor: Sagimet Biosciences

Protocol Number: 3V2640-CLIN-005

Version and Date: Final Version 1, 02June2020

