APPENDIX 1. COVID-19 IMPACT AND DATA HANDLING

COVID-19 impacts on 3V2640-CLIN-005 include, but are not limited to, missed visits, inability to complete certain assessments per the protocol including Week 12 MRI-PDFF data which constitutes the data for the primary efficacy endpoint. In order to collect as much efficacy data on all randomized subjects, subjects were allowed to continue on their treatment beyond Week 12 and have their end of treatment MRI-PDFF performed at any time between Week 11 and Week 16 per protocol Amendment 5. Study drug was not permitted to be continued for more than 16 weeks. The End of Study Visit was scheduled for 4 weeks after the last dose of study drug.

Given the uncertainty of the impact of extended dosing beyond Week 12 on efficacy, the primary and secondary efficacy analyses will be performed excluding subjects who entered extended dosing beyond 12 weeks. Sensitivity analyses that include these subjects will be performed to evaluate the end of treatment efficacy.

The analysis of safety will include all collected data regardless of treatment extension.

An addendum to this SAP will be developed that documents all additional data handling techniques employed to manage COVID impacted data, if needed.

Sponsor: Sagimet Biosciences

Protocol Number: 3V2640-CLIN-005

Version and Date: Final Version 1, 02June2020

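### A missing off-drug (End of Study) liver-fat scan is filled with the end-of-treatment or early-termination scan, which overstates the End of Study effect if fat rebounds

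*SAP*

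**What the plan says.** SAP 7.8 carries the last scan on or after Week 8 forward to a missing Week 12 value, then extends the rule: "MRI-PDFF analyses at other timepoints (e.g., End of Study) will follow similar conventions and use the last-post baseline observation on or after Week 8". SAP 3.1 defines the visit: "End of Study Visit: Visit corresponding to 4 weeks after the end of treatment visit".

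Protocol 7.1 and Table 2 schedule MRI-PDFF before dosing, at Week 11–12 and at Week 16, plus a scan at early termination. Protocol 8.9 places the Early Termination visit within 1 week of the last dose. No Week 8 scan is scheduled.

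Two sets of End of Study results can use the filled value. One is the endpoint in SAP 4.1: "Percent change from baseline in liver fat at End of Treatment and End of Study, as determined by MRI-PDFF". The other is in SAP 8.3.2: "Similar responder analyses will be performed using reduction in liver fat at End of Study in the mITT, ITT, and ATP populations".

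The SAP also limits the rule's reach. SAP 7.8 restricts imputation to the primary and selected secondary MRI-PDFF endpoints and adds: "Sensitivity analyses will be performed excluding data from subjects with missing data (i.e., observed cases approach". The analysis in SAP 8.3.1.2 of whether the effect persists (change from End of Treatment to End of Study) leaves missing data out.

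Protocol 13.2.2 states carry-forward only for missing Week 12 values in the primary and key secondary analyses, and leaves other methods to the SAP. SAP section 9 does not list the extension to End of Study among its changes.

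**The concern.** The End of Study scan shows what remains after the drug is stopped. Carrying the end-of-treatment scan forward assumes the answer, because each filled subject is recorded as having no change off drug.

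Missing scans at this visit are foreseeable. Protocol Table 2, footnote 17, provides that "if the subject is unable to attend both the Week 12 and Week 16 visit, one MRI-PDFP may be performed at any time" between Weeks 11 and 16, with drug continued until the scan if it falls after Week 12. A subject who uses that route has no off-drug scan. SAP Appendix 1 records that "COVID-19 impacts on 3V2640-CLIN-005 include, but are not limited to, missed visits, inability to complete certain assessments per the protocol". Footnote 2 of the same table says "subject participation in the 25 mg cohort is complete", so pandemic-related gaps would fall in the 50 mg cohort and its own placebo subjects.

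At stake is the reading of the End of Study percent-change and responder tables. If fat returns after stopping, they credit the drug with effect that is no longer there.

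**Working it through.** The documents give no figure for End of Study missingness or rebound, so there is no plan figure to reproduce.

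**Inputs from the plan (SAP 3.3).** Planned difference 24 points; SD 30; 30 evaluable subjects per group; planned responder difference 36.7 points.

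**Assumptions.** f = share of active subjects with no End of Study scan. r = share of the effect retained at End of Study. No off-treatment change on placebo. Missingness unrelated to the off-drug value.

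**Step 1: which scan is carried.** Barring an unscheduled scan, the only post-baseline scan before End of Study is the end-of-treatment or early-termination one. The carried value is therefore on drug or within about a week of the last dose.

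**Step 2: bias in percent change.** True End of Study difference = 24r. Carry-forward gives 24[f + (1 − f)r]. Overstatement = 24 × f × (1 − r). With no placebo change, only missingness in the active arm matters.

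| f | r | Overstatement (points) |
|---|---|---|
| 5% | 50% | 24 × 0.05 × 0.5 = 0.6 |
| 10% | 50% | 24 × 0.10 × 0.5 = 1.2 |
| 20% | 50% | 24 × 0.20 × 0.5 = 2.4 |
| 20% | 0% | 24 × 0.20 × 1 = 4.8 |
| any | 100% | 0 |

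The standard error of a difference with 30 per arm is 30 × √(2/30) = 7.7. The 1.2-point and 2.4-point cases are therefore about 0.15 and 0.31 standard errors. If fat kept falling off drug, the sign would reverse.

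**Step 3: responders.** The same form gives 36.7 × f × (1 − r), where r is now the share of the responder difference retained. This need not equal the share of the mean effect retained. Results: 36.7 × 0.10 × 0.5 = 1.8 points; 36.7 × 0.20 × 0.5 = 3.7; 36.7 × 0.20 × 1 = 7.3.

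**Step 4: precision without carry-forward.** The observed-case 95% half-width is 1.96 × 30 × √(1/n₁ + 1/n₂). It is 15.2 points at 30/30, 16.0 at 27/27 (10% missing in both arms) and 17.0 at 24/24 (20%).

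A model fitted to both scans borrows from the end-of-treatment scan. With within-subject correlation ρ and n observed per arm, its variance is approximately 2 × 900 × [(1 − ρ²)/n + ρ²/30]. At an assumed ρ = 0.7:
- n = 27: 1800 × (0.51/27 + 0.49/30) = 63.4, half-width 1.96 × √63.4 = 15.6.
- n = 24: 1800 × (0.51/24 + 0.49/30) = 67.7, half-width 1.96 × √67.7 = 16.1.

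**Step 5: total error.** Root mean squared error, same share missing in both arms: carry-forward = √(60 + bias²), since 2 × 900/30 = 60; observed cases = √(1800/n); two-scan model = square root of the variance in Step 4.

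| f, r | Carry-forward | Observed cases | Two-scan model (ρ = 0.7) |
|---|---|---|---|
| 10%, 50% | 7.8 | 8.2 | 8.0 |
| 20%, 50% | 8.1 | 8.7 | 8.2 |
| 20%, 0% | 9.1 | 8.7 | 8.2 |

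A simulation under the same assumptions (15,000 runs per case) agreed with these values within 0.1. Bias was within 0.15 points of zero for observed cases and for the two-scan model.

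**The case against.** The best defence is that the SAP already answers the persistence question cleanly. Its dedicated End of Treatment to End of Study analysis excludes missing data, and observed-case analyses are planned. What remains is which of two planned versions is the main one, for additional secondary results outside the testing sequence of SAP 7.3. That stands, and it sets the size of this point. A reader might infer that the trial's whole evidence on retained effect is inflated; the documents do not support that.

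On total error, carry-forward beats observed cases at r = 50%. That also stands. The reason to change is to remove a one-directional bias, and it favours the two-scan model over observed cases for percent change.

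The pandemic route is narrower than it first appears. A subject whose single scan falls after Week 12 is an extended doser, kept out of the main analyses (SAP 8.3.1.1, 8.3.2, Appendix 1) and entering only the supplemental ones. For the main tables, the footnote 17 route needs a scan by Week 12 and then no Week 16 scan. Ordinary missed visits remain possible in either cohort.

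A reader might also infer that the rule makes 50 mg look better retained than 25 mg. That would need a particular split of missing scans between cohorts, which the documents do not give. The plan compares each dose with pooled placebo and has no 50 mg versus 25 mg test.

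Finally, the limit to selected secondary endpoints leaves unclear exactly which tables use the rule, and SAP 8.3.2 repeats the imputation only for Week 12. But SAP 7.8 names End of Study expressly, so the ambiguity calls for clarification and does not remove the point.

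**Conclusion.** The point holds as a modest one. As written, SAP 7.8 puts an on-drug or near-on-drug value into a visit defined as 4 weeks after end of treatment. Where the rule is used, the End of Study percent-change and responder results are too favourable if fat rebounds. Under the f and r assumed in the working, the percent-change excess runs from 0.6 to 4.8 points. It is small against an SD of 30 unless many scans are missing and most of the effect is lost within 4 weeks.

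The documents contain no off-treatment liver-fat data, so they do not show that rebound occurs. The primary and key secondary analyses are at Week 12, and neither they nor Type I error control is affected.

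**What to change.** In SAP 7.8, remove carry-forward as the main method at End of Study.
- **Percent change:** make the main analysis a repeated-measures model of the SAP 8.3.2 type, fitted to the End of Treatment and End of Study scans without imputation. SAP 8.3.2 specifies that model for aminotransferases and similar markers, so this extends it to MRI-PDFF. At minimum, use the planned observed-case analysis.
- **Responders:** make the planned observed-case analysis the main one.
- **Carry-forward:** keep it only as a labelled sensitivity analysis, and name the tables that use it.
- **Reporting:** give the number of missing End of Study scans by arm.

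The cost is a short change to SAP 7.8, one added model for percent change, and some precision. The observed-case half-width grows from 15.2 to 16.0 points at 10% missing in both arms and to 17.0 at 20%. The two-scan model recovers about half of that loss at a correlation of 0.7 (15.6 and 16.1), and more if the two scans correlate more strongly. Neither replacement is assumption-free: both still require missingness to be unrelated to the unobserved off-drug value, given what each analysis uses.
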